7.1.2 Biological NCCN and GPS-based risk groups

Biological risk groups, based on NCCN and GPS, are defined as follows:

Very Low: probability of favorable pathology ≥79%

Low: probability of favorable pathology 68-78%

Low-Intermediate: probability of favorable pathology ≤67%

Note that the probability of favorable pathology will be rounded to the nearest whole percent.

7.1.3 Adverse RP pathology

RP pathology assessments will include Gleason score and pathologic T-stage. Adverse pathology is defined as high-grade and/or non-organ-confined disease as shown in the table below, where Gleason Score \leq 3+3 or 3+4 and pT2 is the baseline category and all other categories are compared to the baseline category.

Table 1: Definition of Adverse Pathology

RP Gleason Score	Pathologic T2 Stage	Pathologic T3 Stage
≤3+3	Baseline Category	Non-organ confined
3+4		Disease
Major pattern 4 or	High-grade	High-grade and Non-
any pattern 5		organ confined Disease

High-grade disease at RP is defined as the presence of any major pattern 4 or any pattern 5 at RP.

Protocol Number:	Revision Number:	Effective Date:	Page:
09-023	1.0	2	19 of 28

Non-organ-confined disease is defined as pathologic T-stage (pT) pT3a or pT3b or nodal involvement where pT3a signifies extraprostatic extension (EPE) and pT3b signifies seminal vesicle involvement (SVI).

7.2 Statistical Analysis of Primary Endpoint

Persistence at 1 year will be described as the proportion of patients who remain on AS as of their 12 month visit. Specifically, this is defined as the number of patients who are documented as intervention-free at their 12-month visit (Visit 2) divided by the number of patients who chose AS at Visit 1c. Persistence at 2 years will be calculated in a similar manner. Additional analysis will exclude the subjects who were lost to follow-up or died before the 12-month (Visit 2) and 24-month (Visit 4) visits for analysis of the 1-year and 2-year persistence rates respectively. Exact 95% confidence intervals for proportions will be calculated using the F-distribution method $^{(16)}$.

Additionally, the proportion of men who experienced specific outcomes during surveillance, including definitive treatment, physician-reported biopsy findings, exit from the study, and death from all causes will be calculated as a crude proportion. Similar analyses will be conducted to estimate the proportion of patients who persist on AS by NCCN-based risk group (very low, low, and low-intermediate) and by biological risk group defined by NCCN and GPS (probability of favorable pathology \geq 79%, 68-78%, \leq 67%).

Kaplan-Meier methods will be used to estimate time on surveillance free of definitive treatment. Time zero will be defined as the diagnostic biopsy date and time on surveillance free of definitive treatment will be defined as time from diagnostic biopsy to definitive treatment. Patients who withdraw without evidence of definitive treatment or are lost to follow-up will be censored at the time of their last visit and those who died will be censored at the time of death.

The aforementioned methods have been used in prominent AS literature to assess persistence on AS ⁽¹⁷⁾. Because patients lost to follow-up could be drop-outs due to seeking definitive treatment elsewhere, alternative methods that account for informative censoring will be explored to evaluate the consistency of results.

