4.1.1 Early Termination/Withdrawal Procedures

The following patient situations will result in screen failures and these patients will not be included in any analysis:

- Patients who have signed a consent form, but for whom a sample was not sent to GHI
- Patients who have signed a consent form and had a sample submitted to GHI, but for whom no GPS was generated

Patients who sign a consent form and receive a valid GPS but do not choose either AS or immediate treatment at Visit 1c will be considered unevaluable.

Patients who enter the study on the AS arm, and who subsequently decide to undergo treatment, will be required to complete the End of Study (EOS) visit assessments. Those patients who are Lost to Follow Up (LTFU) will also have the EOS form completed. LTFU patients are defined as those that have had at least 3 contact attempts over a one-month period. Those patients who have been reported deceased or withdraw consent will also have the EOS form completed.

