6. STUDY CALENDAR AND ASSESSMENTS

Site Specific Assessments and Forms:

The following forms will be collected during the course of the study: Site Principal Investigator Initiation Form, Site Principal Investigator Protocol Signature Page, Enrollment Log and Non-Enrollment Log. Instructions for the completion and submission of these forms will be provided by GHI.

Assessments and Forms for each Enrolled Patient:

After a patient consents to participate in this study, the assessments and forms listed in the table below will be completed by the treating physician and submitted to GHI as instructed. The Onco*type* DX Prostate Cancer Assay is expected to report results within a 13-21 day turnaround time upon receipt of the tumor specimen at GHI's laboratory.

Completion of Forms for each Enrolled Patient:

- Data is expected to be entered into the EDC (Electronic Data Capture) system within 5 business days of the patient's visit.
- Queries are expected to be addressed and responded to within 5 days of issue.

Table 1: Study Schema

• Visits 1b and 1c may occur anytime within 4 months of consent (Visit 1a), as is suitable for the patient. Subsequent visits (Visits 2, 3 and 4) are based on the duration from the date of biopsy, not from Visit 1a.

Protocol Number: 09-023	Revision Number: 1.0	Effective Date:	Page: 17 of 28

Assessments	Visit 1a	1b	1c	2 M12	3 M18	4 M24	End of Study
							Juan
Eligibility Criteria	X						
Informed consent	Х						
GPS ordered	X						
Demographics	Х						
Clinical T-Stage and Physician Risk Assessment	Х						
Biopsy ¹	Х			X	X	Χ	X
PSA ¹	X			X	X	X	X
DRE ¹	Х			Х	X	X	Х
FACT-G	Х			X		X	
EPIC-CP	X			X		X	
Decisional Conflict Scale		X ²	χ^3				
Patient informed of GPS result		Χ					
Decisional aids provided	X ⁴	X ⁵					
Physician Treatment Recommendation	X ⁶						
Physician –Patient Shared Decision			X				
Physician perceived value of GPS			X				
Patient perceived value of GPS			X				
Persistence on Active Surveillance				Х	Х	Х	
Regret				Х		Х	
End of Study ⁷							X
Surgical Pathology ⁸				Х			

¹ completed at Visit 1a and any subsequent visit, if new results are available since prior visit

² administered **before** the patient sees the physician and obtains the GPS report.

³ administered at completion of the visit **after** discussing the treatment options with physician

⁴ disease specific decisional aid provided (i.e. AUA Prostate Cancer Brochure)

⁵ Onco*type* DX specific decisional aid provided (i.e. GPS Patient Brochure)

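### Section 7.2 scores a man with no Visit 2 record as non-persistent at 1 year even when later study records show he was untreated at month 12

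*Combined protocol and SAP*

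**What the plan says.** Section 7.2 opens by describing 1-year persistence in general terms, as remaining on AS at the 12-month visit. It then fixes the calculation: the numerator and denominator are men "documented as intervention-free at their 12-month visit (Visit 2) divided by the number of patients who chose AS at Visit 1c". For the second time point, "Persistence at 2 years will be calculated in a similar manner".

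Three other parts of Section 7.2 bear on men without a record:

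- A supplementary calculation: "Additional analysis will exclude the subjects who were lost to follow-up or died before the 12-month" visit, and likewise for the 24-month visit. Consent withdrawals are not named.
- Descriptive proportions for several outcomes, including "exit from the study, and death from all causes will be calculated as a crude proportion".
- A Kaplan-Meier analysis in which "time on surveillance free of definitive treatment will be defined as time from diagnostic biopsy to definitive treatment". For censoring, "Patients who withdraw without evidence of definitive treatment or are lost to follow-up will be censored at the time of their last visit".

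The schedule in Section 6 (Table 1, Study Schema) collects "Persistence on Active Surveillance" at months 12, 18 and 24. It times these visits from the biopsy date and gives no window for them. On loss to follow-up, Section 4.1.1 says: "LTFU patients are defined as those that have had at least 3 contact attempts over a one-month period". Section 7.5 places an analysis of 1-year persistence at the point when all enrolled patients have completed Visit 2. Section 4.1 ends follow-up of AS men at Visit 4.

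**The concern.** The numerator depends on a record at one visit, while the denominator is everyone who chose AS. Nothing in Section 7.2 says what happens when Visit 2 was skipped and a later record answers the question. Being untreated at month 18 or 24 implies being untreated at month 12, so for these men the stated rule gives a result that the study's own data contradict.

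The 1-year rate is half of the primary objective (Section 2.1.1), and the estimates by risk group follow the same method. The 1-year proportion would partly measure visit compliance. Part of any gap between it and the 1-year Kaplan-Meier estimate would be a scoring artefact.

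A smaller mismatch sits beside this. The supplementary analysis removes lost and deceased men but keeps men who withdrew consent, although Kaplan-Meier censors withdrawals without evidence of treatment.

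**Working it through.** **How the rule scores each type of man with no Visit 2 record who is not declared lost**

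| Later record | 1 year, as written | True status at month 12 | 2 years, as written |
|---|---|---|---|
| Untreated on AS at Visit 4 | not persistent | untreated | persistent (contradiction) |
| Untreated at Visit 3, none at Visit 4 | not persistent | untreated | not persistent |
| Definitive treatment dated after month 12 | not persistent | untreated | not persistent if treated before Visit 4 |
| None | not persistent | unknown | not persistent |

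The first three rows are wrong at 1 year. Only the first also reverses between the two time points. The fourth cannot be settled from the data.

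**Inputs**

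- From Section 8: about 300 evaluable AS men and 17% drop-out by 2 years. The stated design reproduces: P(X ≤ 60 | n = 300, p = 0.17) = 0.926 exact and 0.917 by normal approximation, against the stated 90%.
- Assumed, because the plan gives no 1-year rate: 2-year persistence of 83% (1 − 0.17, read as leaving AS for treatment) and a constant hazard. True 1-year persistence is then 0.83^0.5 = 0.911.
- Assumed, because the documents give no missed-visit rate: a share m of 12-month persisters without a Visit 2 record, from 1% to 10%.
- Assumed: a share r of those men who have a later record that settles their status.

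**Reading under the literal rule:** 0.911 × (1 − m)

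| m | 1-year proportion | Men affected (300 × 0.911 × m) |
|---|---|---|
| 0 | 91.1% | 0 |
| 1% | 90.2% | 2.7 |
| 2% | 89.3% | 5.5 |
| 5% | 86.5% | 13.7 |
| 10% | 82.0% | 27.3 |

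Without the constant-hazard assumption, 1-year persistence lies between 83% and 100%. At m = 5% the total loss is then 0.83 × 0.05 = 4.2 to 1.00 × 0.05 = 5.0 points.

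**Reading once later records are used:** 0.911 × (1 − m + m·r), at m = 5%

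| r | 1-year proportion | Coverage of 91.1% by the exact 95% CI |
|---|---|---|
| 0 (literal rule) | 86.5% | 32% |
| 0.5 | 88.8% | 77% |
| 0.8 | 90.2% | 93% |
| 1 | 91.1% | 97% |

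Only the difference from the first row belongs to this defect. With r = 0.5 that is 88.8 − 86.5 = 2.3 points, about 7 men. The rest comes from men with no later record.

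**Side effect of re-scoring year 1 alone.** Suppose 5% of persisters are missed at both visits. The 2-year proportion reads 0.83 × 0.95 = 78.9% under either rule, because no visit follows Visit 4.

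| Comparison | Fall from year 1 to year 2 |
|---|---|
| True | 91.1 − 83.0 = 8.1 points |
| Literal rule at both | 86.5 − 78.9 = 7.7 points (unrounded) |
| Year 1 re-scored, r = 0.5 | 88.8 − 78.9 = 10.0 points (unrounded) |
| Year 1 re-scored, r = 0.8 | 90.2 − 78.9 = 11.3 points |

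The re-scored 1-year figure should therefore not be set against the 2-year proportion.

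**Withdrawals in the supplementary analysis.** Assume 3% lost and a share w withdrawn, both unrelated to treatment. Keeping withdrawals in the denominator gives 0.83 × (1 − w/0.97): 82.1%, 81.3% or 78.7% at w = 1%, 2% or 5%. Excluding them gives 83.0%.

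**The case against.** The strongest reply is that the affected group may be almost empty. A man must have no Visit 2 record, must not be declared lost or leave the study, and must have a later record. No window bars a late contact from being entered as Visit 2. Men who cannot be reached can be classed as lost and then leave the supplementary analysis. Treating an undocumented man as not persisting is also a conservative rule, applied alike at both time points, and no formal test depends on it. Kaplan-Meier, the crude proportions and the exploration of informative censoring stand beside it. All of this is fair, and it keeps the point minor.

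It does not remove the point. A man who skips one visit and returns need not meet the loss definition, so the supplementary analysis keeps him as a failure. The informative-censoring work is motivated by men lost to follow-up, not by skipped visits. The timing in Section 7.5 says when to analyse, not how to score a missing visit. The softer opening sentence of Section 7.2 could allow later records, but the specific definition after it does not.

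The reply is also right that re-scoring only year 1 can overstate the second-year fall. The remedy needs a guard against that.

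A reader might infer three stronger things:

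- **Every man seen later fails and then persists.** Only a Visit 4 record does this.
- **The whole loss at a given missed-visit rate, and the 32% coverage, are due to this rule.** They include men with no later record, whose status the data cannot settle.
- **The Section 8 sample size is undermined.** Section 8 concerns 2 years and does not define drop-out. If its 17% already includes attrition, its probability statement stands.

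**Conclusion.** The point holds as a minor defect in the 1-year half of the primary endpoint. As written, the rule misclassifies men whose later records show they were untreated at month 12, and a man with a Visit 4 record receives contradictory results at 1 and 2 years. The direction is certain: the 1-year proportion is too low, by 0.33 points per such man among 300.

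The size is not known. The 91.1% rests on a constant hazard and on reading Section 8's 17% as leaving AS for treatment; the missed-visit rates and the shares with later records are assumptions. At 5% missed, the correctable part is 2.3 points if half of the men have a later record and 4.6 points (91.1 − 86.5) if all do. The Kaplan-Meier estimate is unaffected. The withdrawal mismatch is a separate, smaller inconsistency, confined to the supplementary analysis.

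**What to change.** 1. **1-year proportion.** Score men with a Visit 2 record as now. Count a man without one as persistent at 12 months if a later visit documents him intervention-free, or if his recorded definitive-treatment date falls after month 12 from biopsy. Leave all others as not persisting.
2. **Reporting.** Treat the 1-year figure from the Section 7.5 interim analysis as provisional, re-score it at study end, and state how many men changed. Report the literal Visit 2-only proportion beside it.
3. **Year 1 against year 2.** Take any such comparison from Kaplan-Meier or from the literal proportions at both times. State that missed Visit 4 records cannot be recovered because follow-up ends there.
4. **Supplementary analysis only.** Also exclude men who withdrew consent without evidence of treatment before the visit, matching the Kaplan-Meier censoring. The primary proportion keeps them as not persisting.

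The cost is a few sentences in Section 7.2 and a short re-scoring step. Persistence is already collected at months 12, 18 and 24, the End of Study form covers withdrawal, and Kaplan-Meier already needs the treatment date. There are two downsides: the interim 1-year figure may rise later, and excluding withdrawals assumes that they resemble the men who stay.

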8. SAMPLE SIZE JUSTIFICATION

The sample size was calculated with the intent of showing a drop-out rate on AS of 20% or less when GPS is incorporated into treatment decisions. A rate of 20-30% is what is reported in the literature ^(17,18). Assuming a true drop-out rate of 17% by 2 years a sample size of 300 patients will be required to achieve 90% probability that the observed drop-out rate will be 20% or less. We expect that if 1200 patients are enrolled, approximately 30%, or 360 of the patients will choose active surveillance and after accounting for patients with insufficient tissue, approximately 300 will be evaluable for the primary endpoint.

Protocol Number:	Revision Number:	Effective Date:	Page:
09-023	1.0	Diceave Date.	22 of 28

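### The additional persistence analysis in Section 7.2 leaves out men lost to follow-up or dead but keeps untreated consent withdrawals as failures, whereas the Kaplan-Meier analysis in the same section censors them

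*Combined protocol and SAP*

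**What the plan says.** For one-year persistence, Section 7.2 takes this numerator: "the number of patients who are documented as intervention-free at their 12-month visit (Visit 2"). The count so obtained is then "divided by the number of patients who chose AS at Visit 1c". The two-year rate follows the same pattern at Visit 4. Nobody leaves this denominator.

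A second proportion is then planned: "Additional analysis will exclude the subjects who were lost to follow-up or died before the 12-month (Visit 2) and 24-month (Visit 4) visits".

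For time on surveillance, the same section says: "Patients who withdraw without evidence of definitive treatment or are lost to follow-up will be censored at the time of their last visit". Deaths are censored at death.

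The study procedures keep the exits apart. In Section 4.1.1, "LTFU patients are defined as those that have had at least 3 contact attempts over a one-month period"; a separate sentence reads "Those patients who have been reported deceased or withdraw consent will also have the EOS form completed". Footnote 7 to the study schema table in Section 6 likewise lists consent withdrawal, death and loss to follow-up (LTFU) as distinct triggers for the End of Study (EOS) form.

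Two further parts of Section 7.2 bear on the point. It plans proportions for definitive treatment and biopsy findings, and "exit from the study, and death from all causes will be calculated as a crude proportion". It also says that methods for informative censoring will be explored, because men lost to follow-up might have gone elsewhere for treatment.

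**The concern.** A man who chose active surveillance (AS) can leave the study untreated in three ways: he is lost, he dies, or he withdraws consent. The additional analysis names the first two and omits the third. The Kaplan-Meier rule names all three and treats withdrawal exactly like loss. The plan gives no reason for the difference, and LTFU cannot be stretched to cover withdrawal, because Section 4.1.1 defines it by contact attempts.

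At stake is the meaning of the additional proportion. As written, part of its non-persistence would be men who left the study with no treatment on record, while other men in the same position are removed. It could then differ from the Kaplan-Meier estimate because of classification and not because of anything that happened on surveillance. The persistence estimates by risk group, which Section 7.2 describes as similar analyses, and the one-year interim analysis in Section 7.5 may inherit the ambiguity.

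**Working it through.** **Step 1. Classification.** How Section 7.2 handles a man with no treatment on record who leaves before the relevant visit:

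| Exit | Primary proportion | Additional proportion | Kaplan-Meier |
|---|---|---|---|
| Lost to follow-up | failure | excluded | censored at last visit |
| Died | failure | excluded | censored at death |
| Withdrew consent | failure | failure | censored at last visit |

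The plan never says in words that a withdrawal is a failure in the additional proportion. It follows from the definitions: he stays in the denominator and has no visit at which he can be documented intervention-free. A man who withdraws after Visit 2 can still count as persistent at one year, so only withdrawals before the visit in question are affected.

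**Step 2. The plan's own figure.** Section 8 states: "Assuming a true drop-out rate of 17% by 2 years a sample size of 300 patients will be required to achieve 90% probability". The event in question is an observed rate of 20% or less. With X binomial (300, 0.17):

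- exact, P(X ≤ 60) = 92.6%;
- normal approximation, Φ(0.03 / √(0.17 × 0.83 / 300)) = 91.7%;
- exact with strictly less than 20%, P(X ≤ 59) = 90.2%.

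The stated 90% is met. Section 8 does not tie this figure to the additional analysis.

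**Step 3. Size of the gap.** From the documents: 300 evaluable AS men and 17%, hence 0.17 × 300 = 51. Assumed: the 17% is treatment only; 15 men lost; 6 dead; and w untreated withdrawals of 1%, 3% or 5% (3, 9 or 15 men). After the planned exclusions, 300 − 15 − 6 = 279 men remain.

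- As written: (51 + w) / 279.
- Withdrawals handled like LTFU: 51 / (279 − w).

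| w | As written | Handled like LTFU | Gap (points) |
|---|---|---|---|
| 3 | 54/279 = 19.4% | 51/276 = 18.5% | 0.9 |
| 9 | 60/279 = 21.5% | 51/270 = 18.9% | 2.6 |
| 15 | 66/279 = 23.7% | 51/264 = 19.3% | 4.3 |

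With 15 men lost or dead in total, instead of 21, the gaps are again 0.9, 2.6 and 4.3 points.

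**Step 4. The reading of 17%.** Section 8 does not define drop-out. If the 51 already include the withdrawals, the additional analysis gives 51/279 = 18.3% as written. Excluding the withdrawals gives (51 − w) / (279 − w): 48/276 = 17.4%, 42/270 = 15.6% and 36/264 = 13.6%. The levels fall, but the gaps are similar, at 0.9, 2.7 and 4.6 points.

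**Step 5. The primary proportion under the Step 3 inputs.** Non-persistence is (51 + 15 + 6 + w) / 300. That is 72/300 = 24.0% with no withdrawals, and 25.0%, 27.0% and 29.0% with 3, 9 and 15.

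**The case against.** The best case for leaving the text alone has four parts.

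*Other analyses already separate treatment from study exit.* This stands. A reader might infer that the additional proportion is the only figure that tells leaving AS from leaving the study. Section 7.2 does not support that: it plans crude proportions for definitive treatment, study exit and death, and its Kaplan-Meier estimate isolates definitive treatment. What is missing is a split of study exit into withdrawal and LTFU. These analyses limit the harm, but they do not change how the additional proportion is computed.

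*The 20% figure is not in play for the main result.* This stands too. A reader might infer from the Step 3 table that the wording moves the trial's main result across 20%. It does not: the wording leaves the primary proportion untouched, and under the same inputs that proportion is 24.0% before anyone withdraws. Only the supporting figure could cross, at 5 withdrawals as written (56/279 = 20.1%) against 25 if they are excluded (51/254 = 20.1%). If the 17% includes withdrawals, it stays below 20% in every case shown.

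*Excluding withdrawals is not neutral.* A man may withdraw because he is seeking treatment elsewhere, and removing him raises apparent persistence. This stands, so the gap is a difference between two classifications and not a measured bias. It does not justify the present split, because Section 7.2 voices the same suspicion about LTFU and still removes those men here. Nor would exclusion make the proportion equal the Kaplan-Meier estimate, since censoring keeps the follow-up before exit and exclusion discards it.

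*The purpose of the additional analysis is not stated.* Correct. That it is meant to set aside exits that are not departures from AS is an inference. The inconsistency between the two rules does not depend on it.

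**Conclusion.** The point holds as a limited one. The additional persistence analysis counts untreated consent withdrawals before the visit as non-persistent, while it excludes loss and death and while the Kaplan-Meier analysis censors withdrawals like losses. Non-persistence in this supporting analysis is 0.9 to 4.3 points higher than under the LTFU rule for withdrawals of 1% to 5%. That range is illustrative: the documents give no withdrawal, loss or death rate, and it reads 17% as treatment only. The classification finding needs none of these assumptions. The primary proportion and the design probability in Section 8 are not altered by this wording.

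**What to change.** - **Reword the exclusion in Section 7.2**, for example: *A supporting analysis omits men who, with no definitive treatment on record, became lost to follow-up, withdrew consent or died before the visit in question.* The condition about treatment keeps a man who was treated first and lost later among the failures.
- **Keep the primary proportion as it is.** It counts every exit as a failure and serves as the conservative bound beside the supporting figure.
- **Split the planned crude proportion for study exit** into untreated withdrawal and LTFU, next to definitive treatment and death. The EOS form is completed for each of these exits, but its fields are not shown, so the sponsor should confirm that it records the reason and the treatment status.
- **Extend the informative-censoring exploration to withdrawals**, since they too may have sought treatment elsewhere.

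The cost is one sentence and one table, with no new visits. The drawback is that the additional estimate becomes less conservative, which is why it should be read beside the primary proportion. The wording is best settled before persistence data are examined.

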3.5 Target Enrollment

3.5.1 This study is targeted to enroll approximately 1200 patients, with no investigator contributing more than 50 patients.

Protocol Number:	Revision Number:	Effective Date:	Page:
09-023	1.0		14 of 28

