3.6 Selection of Treatment Sites

This study will be conducted at approximately 25 large community based urology group practices and 5 academic sites in the United States. Site selection was based on:

- 3.6.1 Projected volumes of new prostate cancer cases per month who meet inclusion criteria
- 3.6.2 Experience with AS
- 3.6.3 The site's ability to conduct clinical studies in prostate cancer, including sufficient research personnel, experience, and infrastructure to obtain patient consent, manage questionnaires, and capture and transmit data to a central research coordinator
- 3.6.4 Expeditious contracting and IRB process

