4. STUDY DESIGN

[figure not shown]
This is a multicenter observational study that evaluates eligible patients who will submit prostate cancer diagnostic biopsy tissues for Onco*type* DX Prostate Cancer Assay testing. At visit 1a, the patient consents to the trial, a pre-assay physician treatment recommendation will be made along with additional assessments defined in Section 6, Table 1, and the assay is ordered. At Visit 1b, the physician will review clinical data, the GPS report and discuss treatment options with the patient. At the following visit, Visit 1c, a shared physician-patient treatment decision (immediate treatment or AS) will be made.

[figure not shown]
Men selecting immediate treatment will be contacted one year from date of diagnosis biopsy to document treatment received and to assess treatment satisfaction and Quality of Life (QoL) metrics.

Men selecting AS as primary treatment will be followed to assess persistence on AS. There is no required or standardized AS protocol for this study and the intensity of surveillance will be at the discretion of the investigator. Patients will not be required, but may undergo a standard TRUS guided surveillance biopsy at one year. In this study, the Onco*type* DX Prostate Cancer Assay will be assessed on the diagnostic biopsy only and will not be assessed on subsequent biopsies. Patients will be queried at 12 and 24 months for assessment of decision satisfaction and Quality of Life metrics.

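### The exact interval for persistence and the 90% probability in Section 8 assume independent men; if persistence varies by site, the interval is too narrow for conclusions beyond the enrolled practices

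*Combined protocol and SAP*

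**What the plan says.** Section 7.2 defines persistence at 1 and 2 years as a single pooled proportion: men documented as intervention-free at the visit, over men who chose AS at Visit 1c. It then states: "Exact 95% confidence intervals for proportions will be calculated using the F-distribution method". Similar analyses are planned by risk group, and Kaplan-Meier is used for time free of definitive treatment. The supporting analyses named in 7.2 deal with loss to follow-up, death and informative censoring. None involves site or investigator.

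Section 8 sizes the study on one common rate, with 17% truly leaving surveillance within 2 years, and concludes: "a sample size of 300 patients will be required to achieve 90% probability that the observed drop-out rate will be 20% or less". It expects that "approximately 300 will be evaluable for the primary endpoint". It mentions no ICC or design effect.

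The men are recruited through "approximately 25 large community based urology group practices and 5 academic sites" (Section 3.6), "with no investigator contributing more than 50 patients" (Section 3.5). On how they are followed, Section 4 says: "There is no required or standardized AS protocol for this study and the intensity of surveillance will be at the discretion of the investigator".

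**The concern.** The F-distribution (Clopper-Pearson) interval reaches its nominal coverage when the count is binomial, meaning independent men with the same probability. Leaving surveillance depends partly on what surveillance finds and on what the physician advises, and the design lets both differ between investigators. Men followed at the same site may therefore have more similar outcomes than men at different sites. In that case the variance of the pooled proportion, seen as an estimate for practice generally, exceeds the binomial variance.

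The study has no comparator arm, so the estimate and its interval carry the primary result. Section 8 sets that result against drop-out rates from the literature, and only 3 points separate the assumed 17% from the 20% bar. The plan neither assumes an ICC nor arranges to estimate one, so a reader of the results could not tell how far the nominal 95% can be trusted.

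**Working it through.** **Inputs from the documents.** True 2-year drop-out 17%, bar 20%, target probability 90%, 300 evaluable men (Section 8); 25 + 5 = 30 sites (Section 3.6), so m = 300/30 = 10 AS men per site on average; exact 95% interval (Section 7.2). Drop-out is treated as the complement of persistence.

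**Assumptions, not in the documents.** ICC from 0.01 to 0.10. Site sizes either equal or moderately unequal, with a coefficient of variation (CV) of 0.57.

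**Step 1: the plan's own figure.** Under independence the standard error is √(0.17 × 0.83/300) = 2.17 points. The normal approximation gives Φ(0.03/0.0217) = 91.7%. The exact binomial gives P(X ≤ 60) = 92.6% and P(X < 60) = 90.2%. The stated 90% therefore reproduces under independence with some slack: the normal formula needs only 1.2816² × 0.17 × 0.83/0.03² = 257.5, or 258 men.

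**Step 2: the planned interval under independence.** With 51 of 300 dropping out (249 persisting), the exact interval for persistence is 78.3% to 87.1%. Its actual coverage at a true rate of 17% is 95.4%.

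**Step 3: what an ICC means here.** The between-site SD of the true drop-out rate is √(ICC × 0.17 × 0.83): 3.8 points at ICC 0.01, 5.3 at 0.02, 8.4 at 0.05 and 11.9 at 0.10. Under a beta distribution, the middle 95% of sites would run from about 4% to 36% at ICC 0.05, and from about 1.5% to 46% at 0.10.

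**Step 4: design effect.** Equal sites: DE = 1 + (m − 1) × ICC = 1 + 9 × ICC. Unequal sites: DE = 1 + ((1 + CV²) × m − 1) × ICC = 1 + 12.26 × ICC. Effective n = 300/DE, and the interval should widen by about √DE.

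**Step 5: results.** Probability and coverage come from beta-binomial simulation with 200,000 runs per row.

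| ICC | Sites | DE | Effective n | P(observed ≤ 20%) | Coverage of planned 95% interval |
|---|---|---|---|---|---|
| 0 | – | 1.00 | 300 | 92.6% | 95.4% |
| 0.01 | equal | 1.09 | 275 | 91.7% | 94.4% |
| 0.02 | equal | 1.18 | 254 | 90.8% | 93.3% |
| 0.03 | equal | 1.27 | 236 | 90.0% | 92.3% |
| 0.05 | equal | 1.45 | 207 | 88.5% | 90.4% |
| 0.10 | equal | 1.90 | 158 | 85.4% | 85.3% |
| 0.01 | unequal | 1.12 | 267 | 91.3% | 94.2% |
| 0.02 | unequal | 1.25 | 241 | 90.1% | 92.6% |
| 0.03 | unequal | 1.37 | 219 | 89.1% | 91.1% |
| 0.05 | unequal | 1.61 | 186 | 87.4% | 88.5% |
| 0.10 | unequal | 2.23 | 135 | 83.5% | 81.9% |

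**Step 6: the interval on the effective sample size.** For 249/300 persisting and equal sites, 78.3–87.1% becomes 78.0–87.2% at ICC 0.01, 77.8–87.4% at 0.02, 77.2–87.9% at 0.05 and 76.2–88.5% at 0.10. This is about 4%, 9%, 20% and 38% wider.

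**The case against.** A reader might infer that the planned intervals simply are too narrow. The documents do not establish that. Section 4 shows that surveillance may differ between investigators. It does not show that drop-out differs, or by how much. The reading also depends on the target of inference. Section 3.6 selects sites on volume, AS experience, research capacity and contracting; it does not sample them. If these sites are taken as fixed, the pooled binomial variance is not too small. Both points stand, and they make the finding conditional.

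A reader might also infer that modest between-site variation already defeats the 90%. It does not, because 300 men leave slack. A shortfall at ICC 0.02 needs strongly unequal sites: at a CV of 0.9 the probability is 89.5%, and nothing in the documents supports that CV. The cap of 50 enrolled, at the planned yield of 25% to 30% (300 to 360 of 1200), limits one investigator to about 12 to 15 AS men, although it does not cap a group practice with several investigators.

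The consequence is limited too. Persistence is described rather than tested, the Section 8 criterion concerns the observed rate, and clustering does not bias that rate when site size is unrelated to drop-out. With about 30 small clusters an estimated ICC is imprecise, which argues against replacing the exact interval.

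What the objection does not remove is the purpose of the study. Section 8 aims at drop-out when the assay is used in treatment decisions, set against published rates. That reaches beyond 30 practices, and the plan has no check on the assumption this requires.

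**Conclusion.** The point holds conditionally. The interval in 7.2 and the probability in Section 8 both assume independence, which the design makes doubtful, and the primary analysis in 7.2 does not test it. If persistence varies by site and conclusions extend beyond the enrolled practices, the interval is too narrow. The loss is small at ICC 0.01 to 0.02 (coverage about 93% to 94%) and material from about 0.05 (about 90% with equal sites, 88.5% with unequal ones). The ICC and the CV are assumptions throughout.

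The stated 90% should not be called wrong. It holds to an ICC of about 0.03 with equal sites or about 0.02 with a CV of 0.57, and falls to roughly 87% to 88% at ICC 0.05. This is a worthwhile, inexpensive improvement to the plan and not a fault that undermines the study.

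**What to change.** In Section 7.2, keep the exact interval and pre-specify beside it a site-clustered 95% interval for 1-year and 2-year persistence, using either a site bootstrap or an intercept-only GEE logistic model with small-sample robust variance. Choose one in advance. Use a site bootstrap for the Kaplan-Meier estimates. Report the estimated ICC and site-level persistence. State that conclusions about practice beyond the enrolled sites rest on the clustered interval.

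In Section 8, note that the 90% assumes no site clustering, and show the probability over an assumed ICC range, for example 0.01 to 0.05.

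The cost is revised wording and a little more analysis on data grouped by enrolling site, with no added patients. The drawbacks are a possibly wider interval and an ICC estimate that will be imprecise with about 30 small sites.
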